7.3 Changes to the protocol

Any changes to the genetic research will comply with the principles described in Section 7.4 of the main body of the protocol.

7.4 Study agreements

The principal investigator at each centre must comply with all the terms, conditions, and obligations of the Clinical Study Agreement for this study. In the event of any inconsistency between this Clinical Study Protocol and the Clinical Study Agreement, the Clinical Study Protocol shall prevail. Specific reference to requirements relating to this genetic research will be included in the study agreement(s).

8. ETHICS

8.1 Ethics review

In addition to documenting Ethics Committee approval of the main study, approval must be obtained for this genetic research and the associated genetic informed consent from the relevant Ethics Committee. It must be clearly stated in the approval that this genetic research is approved. The investigator must submit written approval to AstraZeneca before any patients participate in this genetic research.

8.2 Ethical conduct of the study

The study will be performed in accordance with ethical principles that have their origin in the Declaration of Helsinki and are consistent with ICH/Good Clinical Practice, applicable regulatory requirements and the AstraZeneca policy on Bioethics.

For studies including genetic analysis special precautions are taken as described in section 4.2.2 of this Appendix.

8.3 Informed consent

The genetic component of this study is optional and the patient may participate in other components of the study without participating in the genetic component. To participate in the genetic component of the study the patient must sign and date both the consent form for the main study (non-genetic components of the study) and the genetic component of the study. Copies of both signed and dated consent forms must be given to the patient and the original filed at the study centre. The principal investigator(s) is responsible for ensuring that consent is given freely and that the patients understand that they may freely discontinue from the genetic aspect of the study at any time.

8.4 Patient data protection

All data protection and confidentiality principles, described in the main study protocol, are applicable to this genetic research.

Reference to participation in this genetic research should not be recorded into the patients' general medical records, unless required by local regulations. Instead, all notes should be kept within the clinical study records.

Due to the exploratory nature of this genetic research, there will be no routine communication of results to patients. Bristol-Myers Squibb or AstraZeneca will not provide individual genotype results to patient, any insurance company, any employer, their family members, general physician or any other third party, unless required to do so by law.

Extra precautions are taken to preserve confidentiality and to prevent genetic data from being linked to the identity of the patient. However, it must be recognised that there are exceptional circumstances where individuals may see both genetic data and a patients personal identifier, for example in the case of a medical emergency, when AstraZeneca Physicians and investigators might know the patient's identity and might have access to the genetic data, or during regulatory audit where designated authorities must be permitted access to the relevant files.

With respect to optional blood sample donation, the only information that will be recorded in the eCRF and clinical database will be information related to the provision of informed consent for genetic research and sample collection information. No genotypic data derived from samples collected in this study will be stored in the main clinical database. Genotypic data will be stored in the Bristol-Myers Squibb secure database or another secure database, separate from that used for the main study. Some or all of the dataset from the main study may be duplicated within the Bristol-Myers Squibb secure database to facilitate exploratory genetic analyses.

1. CASE IDENTIFICATION AND MANAGEMENT OF DECREASED RENAL FUNCTION

The evaluation of renal function is an important part of the overall safety assessment in the dapagliflozin clinical development program. In order to standardize the definition and management of decreased renal function, the following guidelines has been developed:

- a) **For patients with baseline creatinine of <1.4 mg/dl (123 µmol/L), an absolute increase in serum creatinine level of ≥ 0.5 mg/dl (44 µmol/L) from baseline based on central laboratory results**

- b) **For patients with baseline creatinine of ≥ 1.4 mg/dl (123 µmol/L), an absolute increase in serum creatinine level of ≥ 1.0 mg/dl (88 µmol/L) from baseline based on central laboratory results**

In either of these circumstances, the investigator should consider evaluating the patient for potentially reversible causes of renal dysfunction including but not limited to:

1. concurrent use of NSAIDS, antibiotics, or other medications known to affect measures of serum creatinine
2. volume depletion
3. urinary tract infection
4. obstructive uropathy

Patients should return for repeat central laboratory testing as soon as possible, no later than 7 days after the abnormal result. Study drug should be interrupted pending the results of repeat testing. If after interruption the serum creatinine value remains above the increase limit described above (³0.5 mg/dl or ³1.0 mg/dl above baseline), the patient should permanently discontinue the medication and be withdrawn from the study (in which case an Adverse Event must be reported).

If after study drug interruption the serum creatinine value has decreased to below the increase limit (<0.5 mg/dl or <1.0 mg/dl above baseline), study drug can be re-started if appropriate in the investigator's judgment and after consultation with the study delivery team physician. If study drug is re-started, the patient should return for a follow-up central lab serum creatinine 7-14 days after re-start, although more frequent assessments may be done at investigator discretion. If the patient restarts study drug and the serum creatinine value increases again to the increase limit (³0.5 mg/dl or ³1.0 mg/dl above baseline), the patient should permanently discontinue the medication and be withdrawn from the study (in which case an Adverse Event must be reported).

Clinical Study Protocol Appendix H

Drug Substance	Dapagliflozin
Study Code	D1690C00006
Edition Number	3
Date	

1. ALGORITHM ON MANAGEMENT OF SUSTAINED ELEVATED LIVER SAFETY ABNORMALITIES

The monitoring for liver safety will be performed using the serum levels of AST, ALT and TB (see Figure 1 algorithm flow chart).

Patients with central laboratory ALT and/or AST >3 ULN will be scheduled for a follow-up visit within 3 days following receipt of the initial laboratory results, to obtain repeat central laboratory ALT, AST, TB and Alkaline Phosphatase (ALK-P). In the event that the repeat laboratory assessments cannot be obtained within 3 days, the Investigator is encouraged to discuss possible alternatives with the Sponsor. Patients should remain on study medication until confirmatory results are obtained, unless otherwise contraindicated.

- **If the repeat ALT and AST are ≤ 3 ULN**, subject should continue in the double-blind treatment according to their original visit schedule unless otherwise contraindicated.
- **If the repeat ALT and/or AST are >3 ULN but ≤ 8 ULN and TB ≤ 1.5 ULN**, the subject's medical history, including details of risk factors for liver diseases should be evaluated for potential underlying etiologies. In addition, specialized blood sampling will be performed to evaluate liver function as well as identify potential causes of laboratory elevation(s). The Investigator should continue to monitor the subject's liver tests every 3 days following receipt of the prior laboratory results until the ALT and AST are ≤ 2 ULN or until ALT and AST are at or below baseline levels. The frequency of retesting can decrease to once a week or less if abnormalities stabilize and the subject is asymptomatic. Patients should remain on study medication unless confirmatory results indicate that a criterion for discontinuation has been met or continuing study medication would be otherwise contraindicated.

Patients must be discontinued from the study if an initial and repeat confirmatory laboratory tests meet any of the following criteria:

- **ALT and/or AST are >3 ULN and TB >1.5 ULN**
- **ALT and/or AST are >5 ULN for ≥ 14 consecutive days, at any time after initial confirmatory results**
- **ALT and/or AST are >8 ULN**

Note: See below for discontinuation procedures.

Guidance on Assessment of Hepatic Laboratory Abnormalities

The following is presented to assist in the evaluation and management of hepatic laboratory values. It is not intended to supplant Investigators' clinical judgment.

Patients who experience ALT and/or AST values >3 ULN confirmed with a repeated test will have the following performed within 3 days of the confirmed laboratory results:

- AE assessment
- Physical examination for jaundice and other signs of liver diseases
- Review of relevant risk factors and current history focusing on possible causes of
- the increased ALT and/or AST and/or TB, including:
- Use of suspect concomitant medication [including over-the-counter (i.e., acetaminophen/paracetamol), herbal and vitamin preparations]
- Recent alcohol consumption or recreational drug / narcotic use
- Recent unaccustomed physical exertion
- Occupational or environmental exposure to hepatotoxins
- Other conditions which may cause liver diseases or which may cause abnormal test results
- Specialized Liver Panel (see below)

Additional information, including but not limited to completion of supplemental eCRFs, may be requested for certain adverse events and/or laboratory abnormalities which are reported/identified as part of the hepatic safety surveillance.

For patients who are discontinued from the study as a result of sustained elevated liver safety abnormalities as described above, study medication will be discontinued, the Sponsor notified and the early termination (End-of-Treatment) visit performed within 3 days of the confirmed laboratory results. Additional blood sampling must be done in conjunction with an early termination (End-of-Treatment) visit, in addition to the procedures noted above. A “Liver Discontinuation” visit laboratory kit, in addition to the Specialized Liver Panel kit as noted below, will need to be used to collect recommended blood samples. Additionally, supplemental (unscheduled) visit eCRF pages as well as supplemental eCRFs will need to be completed to collect “Liver Discontinuation” information. Patient should also be scheduled for a Follow-up visit (i.e. procedures of Visit 19) weeks after discontinuation of investigational product. A referral consultation to a hepatologist or gastroenterologist (specializing in liver abnormalities) should be obtained. Any additional tests and/or examinations should be carried out at the discretion of the Investigator. Any further investigations and laboratory results for patients with abnormal laboratory values at the safety follow-up visit should be made available to the Sponsor upon request.

Following the early termination (End-of-Treatment) visit, the Investigator should continue to monitor the subject’s liver tests every 3 days following receipt of the prior laboratory results until the ALT and AST are ≤ 2 x ULN or until ALT and AST are at or below baseline levels. The frequency of retesting can decrease to once a week or less if abnormalities stabilize and the subject is asymptomatic.

Specialized Liver Panel

For **all patients** who are being monitored frequently as a result of confirmed AST and/or ALT >3 ULN, additional central laboratory tests (Specialized Liver Panel) will be performed within 3 days of receipt of confirmatory results. These laboratory tests will study the possible causes of the increased ALT and/or AST and/or TB, and may include, but are not limited to, the following tests:

- Hepatitis A IgM
- Hepatitis BsAg
- Hepatitis B Core Ab IgM
- Hepatitis C virus RNA
- Hepatitis C Ab
- Hepatitis E IgM
- Epstein-Barr Virus (EBV) IgM Ab
- Lactate Dehydrogenase (LDH)
- Gamma-glutamyl-transpeptidase (GGT)

- Carbohydrate deficient transferrin (CDT)
- Prothrombin time (PT/INR)
- Iron Panel - iron, ferritin, total iron binding capacity (TIBC)
- Immunology Panel including Antinuclear Antibody (ANA), Anti-Smooth Muscle Antibody (SMA) and Anti-Liver/Kidney Microsomal Antibody (Anti-LKM)
- Anti-tissue Transglutaminase Antibody

[figure not shown]
Liver Discontinuation Panel

For patients who are discontinued from the study as a result of sustained elevated liver safety abnormalities, **additional** central laboratory tests will be performed at the time of Early Termination (End-of-Treatment) visit. Similar to the Specialized Liver Panel, these laboratory tests will study the possible causes of the increased ALT and/or AST and/or TB, and may include, but are not limited to, the following tests:

- Cytomegalovirus (CMV) IgM Ab
- Herpes Simplex Virus (HSV) 1 and 2
- Ceruloplasmin
- Toxoplasmosis
- Alpha-1 antitrypsin

For specific details regarding the Specialized Liver Panel and the Liver Discontinuation Panel laboratory tests, refer to the Central Laboratory Manual for this study..

Figure 1 Sustained elevated liver safety abnormalities flow chart

^a In subjects with repeat ALT or AST > 3X ULN, only subjects with TB ≤ 1.5X ULN at Step 1 should be followed according to Step 2b. Subjects with an initial TB and confirmatory repeat TB > 1.5X ULN should be followed according to Step 2d.

^b See above for details on additional assessments to be performed (AE assessment, PE, review of current medical history including focused review of risk factors for liver diseases and collection of blood samples [specialized liver panel for Step 2b and c; specialized liver panel and liver discontinuation panel for Step 2d and e])

^c Confirmatory repeat AST, ALT, ALK-P and TB should be obtained every 3 days following receipt of prior laboratory results, until the ALT and AST are ≤ 2xULN or until ALT and AST are at or below baseline levels. The frequency of retesting can decrease to once a week or less if abnormalities stabilize and the subject is asymptomatic.

Clinical Study Protocol Appendix I

Drug Substance	Dapagliflozin
Study Code	D1690C00006
Edition Number	1
Date	

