Patients with type 2 diabetes on at least 30 IU of insulin per day for at least 8 weeks prior to enrolment, with or without OADs with known HbA1c values $\geq 7,5\%$ and $\leq 10,5\%$ will provide informed consent and submit laboratory samples. Patients on metformin therapy should be on at least 1500 mg/day of metformin or at the maximum tolerable dose for a period of at least 8 weeks prior to enrolment. Patients on other OAD medications should be on at least half maximum daily recommended dose of the OAD for a period of at least 8 weeks prior to enrolment. Patient will be provided with a glucometer and a patient diary and be instructed to record their daily SMBG as well as insulin use during the next two weeks. Patients will be instructed to continue their current insulin and if applicable any ongoing OAD therapy at the same dose level during enrolment period.

24-week double-blind treatment period (Visit 2–9; week 0 to week 24)

If all lab inclusion criteria for V1 are met, Visit 2 should occur two weeks after visit 1. All further applicable inclusion and exclusion criteria will be checked and the mean daily insulin dose will be calculated by the investigator. The calculated mean daily insulin dose is an average total daily insulin dose used over the last seven documented days. Eligible patients with at least 30 IU calculated mean daily insulin dose will be randomized if the daily insulin requirements over the past seven days with insulin dose documentation does not vary more than 10% of the calculated mean daily insulin dose on more than one occasion. (For example for a patient whose calculated mean daily insulin dose is 50 IU, daily doses may not be <45 and >55 IU on more than one occasion within the past seven days with insulin dose documentation).

Eligible patients will be randomized in a 1:1:1:1 ratio to receive either dapagliflozin at 2.5 mg, 5 mg, 10 mg or placebo once daily. Patients will return for visits 1 week after start of treatment and then approximately every 4 weeks to assess efficacy and safety of the treatment. The patients will be instructed to record their fasting SMBG as well as insulin use daily. The patients will further be instructed to always self-monitor plasma glucose in case of symptoms suggestive of hypoglycaemia and to register any signs of hypoglycaemia in the supplied diary. During the study treatment the patients will be instructed to keep their insulin (and if applicable OAD) dose unchanged.

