After 24 weeks of double-blind treatment, patients will continue in the randomized double-blind extension period with the same treatment given as at the end of the 24-week double-blind treatment period. Patients will return for visits approximately every 8 weeks to assess efficacy and safety of the treatment. The patients will be instructed to record their fasting SMBG as well as insulin use daily. The patients will further be instructed to always self-monitor plasma glucose in case of symptoms suggestive of hypoglycaemia and to register any signs of hypoglycaemia in the supplied diary. During the study treatment the patients will be instructed to keep their insulin (and if applicable OAD) dosage unchanged.

Up-titration is defined as an increase in mean daily insulin dose that meets both of the following criteria:

1. the increase in insulin dose is more than 5 IU (i.e. 6 IU or greater)

and

2. the increase in insulin dose is greater than 10% of the baseline insulin dose.

Any insulin dose changes (even if more than 5 IU/ day or more than 10% of the mean daily insulin dose at baseline) during hospitalisation is not considered as an up-titration as long as the insulin dose change is not for a period of more than 10 days and the primary reason for hospitalisation is not management of the patient's glycaemic control. Similarly, if insulin requirement has increased temporarily, e.g. due to an infection, it will not be considered an up-titration even if the insulin dose increase is more than 5 IU or more than 10 % of the baseline mean daily insulin dose as long as such an increase is for a period of not more than 10 days and the insulin dose is expected to return to the baseline level once the precipitating condition has resolved.

Up-titration of the insulin dose during the 24-week double-blind extension period shall be considered by the investigator under the following circumstances:

- if HbA1c measured by central laboratory exceeds 8% at any point of the 24 weeks double-blind extension period

or

- if the FPG measurement taken at the site visits exceeds 180 mg/dl (9.9 mmol/l) and this FPG result is confirmed by both the central laboratory and a repeat FPG measurement at the site at a return visit within 72 hours

or

- if at least 3 fasting SMBG diary measurements from the past 7 days exceed 180 mg/dl (9.9 mmol/l). Diary fasting SMBG values that meet these criteria should be recorded in the eCRF.

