Randomized patients who discontinue early should complete the procedures described for visit 18 (end of treatment period) immediately following discontinuation of study drug. Thereafter patients should return for the 3 week follow up visit so that visit 19 procedures can be completed.

Long-term, double-blind extension period II (Visits 13–18, Weeks 49-104)

After the long term double blind extension period I patients, who

- are still on active study treatment
- and have not developed any reason for study discontinuation

will be asked if they would like to continue the study for another 56 weeks and will sign an informed consent form. All patients randomised to placebo, dapagliflozin 2.5 mg or 10 mg treatment at visit 2 will continue the double-blind extension period II with the same treatment. All patients randomised to dapagliflozin 5 mg will be switched to 10 mg dapagliflozin without breaking the blind.

The patients will be instructed to record their fasting SMBG as well as insulin use daily. The patients will further be instructed to always self-monitor plasma glucose in case of symptoms suggestive of hypoglycaemia and to register any signs of hypoglycaemia in the supplied diary. During the study treatment the patients will be instructed to keep their insulin (and if applicable OAD) dosage unchanged. Patients will contact the investigator 1 week after visit 12 for a telephone visit. During this phone call the investigator will discuss whether the current insulin dose is still adequate and whether there have been any changes in AEs and concomitant medication. The patient will then come in 3 weeks later for the next regular site visit (visit 14). After that patients will return for visits every 13 weeks to assess efficacy and safety of the treatment..

Up-titration of the insulin dose during the long-term, double-blind extension period II should be considered by the investigator under the following circumstances:

- >7.5% at V14,V15
- >7,0% at V16,V17,V18

Insulin dose should not be uptitrated if both the following scenarios are met:

1. A patient has experienced unexpected hypoglycemic event/s
and
2. An uptitration of insulin may put the patient at an increased risk of hypoglycaemia in the clinical opinion of the investigator.

An unexpected hypoglycemic event is an hypoglycemic event that cannot be explained by circumstances such as missing a meal, or extensive physical exertion.

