Erythrocyte mean corpuscle volume	X	X	X	X	X	X	X	X	X	X	X	X		X	X	X	X	X	X	
Erythrocyte mean corpuscle haemoglobin concentration	X	X	X	X	X	X	X	X	X	X	X	X		X	X	X	X	X	X	
Reticulo-cytes	X	X	X	X	X	X	X	X	X	X	X	X		X	X	X	X	X	X	
White blood cell count and differential	X	X	X	X	X	X	X	X	X	X	X	X		X	X	X	X	X	X	
Platelet count	X	X	X	X	X	X	X	X	X	X	X	X		X	X	X	X	X	X	
Clinical chemistry (serum)																				
Aspartate Aminotransferase (AST, SGOT)	X	X	X	X	X	X	X	X	X	X	X	X		X	X	X	X	X	X	
Alanine Aminotransferase (ALT, SGPT)	X	X	X	X	X	X	X	X	X	X	X	X		X	X	X	X	X	X	
Alkaline Phosphatase (AP)	X	X	X	X	X	X	X	X	X	X	X	X		X	X	X	X	X	X	
Creatine Kinase (CK)	X	X	X	X	X	X	X	X	X	X	X	X		X	X	X	X	X	X	
Total Bilirubin (TB)	X	X	X	X	X	X	X	X	X	X	X	X		X	X	X	X	X	X	
Blood Urea Nitrogen (BUN)	X	X	X	X	X	X	X	X	X	X	X	X		X	X	X	X	X	X	
Electrolytes ^g	X	X	X	X	X	X	X	X	X	X	X	X		X	X	X	X	X	X	
Total protein	X	X	X	X	X	X	X	X	X	X	X	X		X	X	X	X	X	X	
Albumin	X	X	X	X	X	X	X	X	X	X	X	X		X	X	X	X	X	X	

Visit	1	2	3	4	5	6	7	8	9	10	11	12	13	14	15	16	17	18	19
Study Week	-2	0	1	4	8	12	16	20	24	32	40	48	49	52	65	78	91	104	107
Uric acid	x	x	x	x	x	x	x	x	x	x	x	x		x	x	x	x	x	x
Serum Creatinine (SCr), calculated creatinine clearance (Cockcroft-Gault formula) ^a	x	x	x	x	x	x	x	x	x	x	x	x		x	x	x	x	x	x
Serum Cystatin C			x							x		x				x		x	x
Serum Bone Metabolism Marker (Parathyroid Hormone (PTH) and 25-hydroxy vitamin D)			x							x		x				x		x	x
Follicle Stimulating Hormone (FSH)	x																		
TSH ^e	x																		
Hepatitis Screen Panel ^f	x																		
Urinalysis																			
Glucose ^b	x	x	x	x	x	x	x	x	x	x	x	x		x	x	x	x	x	x
Blood by dipstick ^c	x	x	x	x	x	x	x	x	x	x	x	x		x	x	x	x	x	x
Albumin	x	x	x	x	x	x	x	x	x	x	x	x		x	x	x	x	x	x
Total protein	x	x	x	x	x	x	x	x	x	x	x	x		x	x	x	x	x	x
Creatinine	x	x	x	x	x	x	x	x	x	x	x	x		x	x	x	x	x	x
Calculated Urinary albumine: creatinine ratio (UACR)	x	x	x	x	x	x	x	x	x	x	x	x		x	x	x	x	x	x
Calculated total protein : creatinine ratio	x	x	x	x	x	x	x	x	x	x	x	x		x	x	x	x	x	x
Pregnancy test ^d	x	x	x	x	x	x	x	x	x	x	x	x		x	x	x	x	x	x

a Creatinine clearance will be calculated by the method of Cockcroft and Gault.

b Results will be blinded.

c Microscopy if dipstick positive for blood.

d Urine or serum pregnancy test (see section 4.7.1.2)

Revised Clinical Study Protocol
Drug Substance Dapagliflozin
Study Code **D1690C00006**
Edition Number 5
Date

- e If abnormal, measure free T4.
- f Includes Hepatitis B viral antibody IgM, Hepatitis B surface antigen and Hepatitis C virus antibody

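### Appendix H lets liver retesting on study drug fall below weekly with no stated minimum above 5x ULN, so the 14-day stop at that level can be recognised late

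*Protocol*

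**What the plan says.** Appendix H, section 1, has one branch for patients who have a confirmed elevation and stay on drug: "repeat ALT and/or AST are >3 ULN but ≤ 8 ULN and TB ≤ 1.5 ULN" (TB is total bilirubin). These patients are retested 3 days after each result arrives, until ALT and AST are at most 2x ULN or back to baseline. The schedule may then be relaxed: "The frequency of retesting can decrease to once a week or less if abnormalities stabilize and the subject is asymptomatic". Footnote c of the flow chart in the same appendix repeats this permission unchanged.

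On treatment the rule is: "Patients should remain on study medication unless confirmatory results indicate that a criterion for discontinuation has been met". One of the mandatory criteria is ALT or AST above 5x ULN for at least "14 consecutive days, at any time after initial confirmatory results". Sections 3.3.3 and 3.3.5.1 repeat that criterion and refer to Appendix H for further guidance. They give no retest schedule for the 14 days.

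Outside Appendix H, ALT and AST are drawn at the scheduled site visits (Table 6). After the week 1 visit the spacing is "then approximately every 4 weeks to assess efficacy and safety of the treatment" in the first 24 weeks. In extension period I: "Patients will return for visits approximately every 8 weeks to assess efficacy and safety of the treatment". In extension period II, after the week 52 visit: "After that patients will return for visits every 13 weeks to assess efficacy and safety of the treatment".

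**The concern.** The on-drug branch is capped at 8x ULN, but the permission to test less often has no limit at 5x ULN. A patient without symptoms whose ALT sits steadily at, say, 6x ULN qualifies for less frequent testing. If that steadiness lasts 14 days, the same patient must stop the drug. Because the drug continues until a result shows that a criterion is met, the interval between draws decides when the stop happens.

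What is at stake is extra exposure in the patients for whom the criterion was written. Appendix I, section 4, reports ALT above 3x ULN in 6/402 and 3/405 dapagliflozin patients against 0/75 and 0/136 on placebo, and says that more data are needed to judge the importance of this. Section 6.7 provides no data monitoring board, so the patient-level rule carries more weight. Efficacy estimates and hepatic adjudication are not affected.

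**Working it through.** The plan gives no figure to reproduce. The check is a count of days to the first draw that can show 14 days above 5x ULN.

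**Inputs.** Results reach the site within 72 hours (Section 4.7.2.1). The default retest is 3 days after receipt (Appendix H). Scheduled ALT/AST draws fall at weeks 0, 1, 4, 8, 12, 16, 20, 24, 32, 40, 48, 52, 65, 78, 91 and 104 (Table 6). Assumption: day 0 is the first draw above 5x ULN and is taken at a scheduled visit.

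**Default schedule.** The interval is up to 3 + 3 = 6 days, giving draws on days 0, 6, 12 and 18. The first draw at or after day 14 is day 18.

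**Weekly retesting.**
- Step-down after day 6: draws on days 13 and 20, so 20 − 18 = +2 days.
- Step-down after day 12: draw on day 19, so 19 − 18 = +1 day.
- If the laboratory reports faster, the default is earlier and the difference can be somewhat larger. With a 2-day turnaround the default draws are days 0, 5, 10 and 15. Weekly after day 5 gives days 12 and 19, so 19 − 15 = +4 days.
- Draws 7 days apart can never put the first draw at or after day 14 later than day 20.

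**Less than weekly.** The text names no further interval. If nothing were drawn before the next scheduled visit, the bound would be the visit gap:

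| Period | Nominal gap | Less default day 18 |
|---|---|---|
| Weeks 4–24 | 4 × 7 = 28 days | +10 days |
| Weeks 24–48 | 8 × 7 = 56 days | +38 days |
| Weeks 52–104 | 13 × 7 = 91 days | +73 days |

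**Other reading of the clock.** The criterion can be read as counting from the confirmatory draw, here day 6. The threshold is then 6 + 14 = day 20 and the default draw is day 24. Weekly after day 12 gives days 19 and 26, so 26 − 24 = +2 days. The outer bounds become 28 − 24 = +4, 56 − 24 = +32 and 91 − 24 = +67 days.

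**How many patients.** Appendix I, section 4, reports one dapagliflozin patient with ALT above 5x ULN in each of two 24-week studies: (1 + 1)/(402 + 405) = 2/807 = 0.25% (exact 95% interval 0.03% to 0.89%). Section 6.5 gives 808 randomised, and equal allocation to four arms puts 808 × 3/4 = 606 on active drug. Assuming the same rate, 606 × 0.00248 = 1.5 patients per 24 weeks (0.2 to 5.4) exceed 5x ULN at any time. Those who stay between 5x and 8x ULN for 14 days, without symptoms and with retesting relaxed below weekly, are fewer. The protocol gives no figure for them.

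**The case against.** The strongest point is that the flow chart is not visible. Its footnotes mention Steps 2b and 2c with the same liver panel, while the running text has only one confirmed on-drug branch, so Step 2c may carry a separate rule for this range. That lowers confidence. It does not remove the point, because the permission stands in the running text and a tighter figure would disagree with it.

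Second, the relaxation is optional and requires both stable values and no symptoms. Judging stability takes several results, by which time day 14 is near, and an investigator who applies the stop has to count the days. This stands: the text allows late recognition but does not cause it.

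Third, a reader might infer that the plan sends such patients back to visits 8 or 13 weeks apart. No sentence says so. Appendix H returns patients to the original visit schedule only when the repeat values are at most 3x ULN. The branch at issue calls for continued monitoring until values reach 2x ULN or baseline. The +38 and +73 days are therefore arithmetic limits only.

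Fourth, a reader might see a double standard in the 7-day limit for repeat creatinine in Appendix G. That limit governs the first repeat. The liver equivalent is 3 days, which is stricter.

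Other safeguards also hold. Confirmed values above 8x ULN, or above 3x ULN with total bilirubin above 1.5x ULN, require a stop with no 14-day condition. Section 3.3.5.1 also allows discontinuation on safety grounds at any time.

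**Conclusion.** The point holds in a narrow form. For patients on drug above 5x and up to 8x ULN with total bilirubin at most 1.5x ULN, the visible text of Appendix H permits retesting less often than weekly with no minimum, beside a mandatory stop that depends on 14 consecutive days. Weekly testing is adequate, costing about 2 days at the 72-hour turnaround. Only the permission to go below weekly needs correcting.

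It would be too strong to say that the stop would be missed: the next result above 5x ULN still triggers it. Nor do the documents show that any patient would have been affected, since the elevations in Appendix I were transient. The count of about 1.5 patients assumes that the rate in two studies of other populations carries over, and it is a ceiling for the affected group under that assumption. Confidence is medium because the flow chart is not visible. This is a cheap improvement for patient safety.

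**What to change.** In the on-drug branch of Appendix H, section 1, and in footnote c of its flow chart, add: *While the patient is on study drug with ALT or AST >5x ULN, retesting must be at least weekly, with a central laboratory draw on or as soon as possible after day 14 of the period >5x ULN.* State whether that period starts at the initial or at the confirmatory draw, since the present criterion can be read either way. Make the flow chart consistent, including Step 2c. Leave the similar sentence on monitoring after the early termination visit unchanged: those patients are off drug, so it cannot delay a stop.

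The cost is a one-sentence change in two places, one clarification of the clock, and a few extra blood samples in very few patients.
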